6.2 MABTHERA

Rituximab (MabThera®) is a genetically engineered chimeric murine/human monoclonal antibody, which binds specifically to CD20, a B-lymphocyte differentiation antigen on pre-B and mature B-lymphocytes. In June 2006, the United States (US) Food and Drug Administration had approved MabThera for RA (Food and Drug Administration, 2006). In June 2006, the European Medicines Agency (EMA) approved the use of rituximab for the same indication. The RA indication was updated by Variation EMEA/H/C/165/II/65 (EMA, 2010). The current European Union (EU) approved label authorises MabThera in combination with methotrexate for the treatment of adult patients with severe, active RA who have had an inadequate response or intolerance to other disease-modifying anti-rheumatic drugs including one or more tumour necrosis factor (TNF) inhibitor therapies.

In March 2013, the EMA approved a new non-oncology-related indication, allowing the use of MabThera in combination with glucocorticoids for the induction of remission in adult patients with severe, active GPA (Wegener's) and MPA (EMA, 2013a). Rituximab is also approved for several oncology conditions, but these indications are not the focus of this study.

This protocol addresses the 2 EU follow-up measures (FUMs) following approval of Variation EMEA/H/C/165/II/65 for MabThera use in RA.

1. FUM no. 68 (Clinical): Drug Utilisation Study to Assess Off-Label Use

There is concern regarding off-label use of MabThera, in particular that rheumatologists and other physicians may prescribe MabThera for systemic lupus erythematosus (SLE) and lupus nephritis (LN). The EMA Committee for Medicinal Products for Human Use (CHMP) FUM (Clinical) No. 68 from Procedure No. EMEA/H/C/165/II/65 states, 'Given the extensive off-label potential of MabThera, the MAH [Marketing Authorisation Holder] should submit a European drug utilisation study protocol to the CHMP'.

2. FUM No, 71.1 (Pharmacovigilance): Evaluation of Receipt, Use, and Impact of the Patient Alert Card (PAC) on Infections, Including Progressive Multi-focal Leukoencephalopathy (PML)

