8.3 VARIABLES

Medical Record Data

The site will abstract information from the medical record for each of the DUS consenting patients and will enter the abstracted information in an electronic case report form (eCRF):

- Study ID (identification), age, sex
- Condition for which MabThera has been prescribed (via checklist):

- RA
- Ankylosing spondylitis
- Psoriatic arthritis
- Undifferentiated spondyloarthritis
- Juvenile idiopathic arthritis
- SLE
- Systemic vasculitis
- Inflammatory myopathies
- Behçet disease
- Sjögren syndrome
- Nephrotic syndrome
- Reason for MabThera prescription:
 - Failure of previous treatment
 - Adverse events (AEs) under previous treatment
 - Compassionate use
- Date of first diagnosis of the condition
- For patients with RA, severity of RA as measured with the DAS28 (28-joint Disease Activity Score). To calculate the DAS28, the following items will have to be abstracted from the medical record:
 - C-reactive protein level
 - Erythrocyte sedimentation rate
 - Number of tender joints
 - Number of swollen joints
 - Global assessment of patient's general health on the visual analogue scale (VAS) (0–100)
 - Presence of extra-articular involvement
- MabThera dosage for the most recent infusion and number of MabThera infusions in the past 2 years
- Other current and previous anti-inflammatory medication including biological agents other than MabThera
 - Methotrexate (key variable for on- or off-label classification of MabThera use)

- Glomerulonephritis
- Multiple sclerosis/neuromyelitis optica
- Pemphigus vulgaris
- Polydermatomyositis
- Mixed connective tissue disease
- Wegener's GPA/ MPA
- Eosinophilic GPA
- Other (specify)

- Immunosuppressives: prednisolone, glucocorticoid bolus therapy, methylprednisolone, methotrexate, cyclophosphamide, azathioprine, mycophenolate mofetil, intravenous immunoglobulin, plasmapheresis, other immunosuppressives (specify)
- Non-steroidal anti-inflammatory drugs (NSAIDs), including cyclooxigenase (COX)-2 inhibitors
- Biological agents:
 - TNF-alpha inhibitors (key variable for on- or off-label classification of MabThera use): etanercept, infliximab, adalimumab, golimumab, certolizumab pegol, ocrelizumab
 - Interleukin inhibitors: tocilizumab, anakinra
 - Abatacept
 - Janus kinase (JAK) inhibitor: tofacitinib
 - Other biological agents (specify)

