A "data not available" response will be available where appropriate for those record abstraction items for which data may be missing from patient records. This type of response will help reduce missing data and will document the overall gaps in record keeping.

A brief pilot test of the translated version of the abstraction form will be conducted in each country, and the abstraction form in one or more countries may be adjusted based on the results of this pilot.

A draft version of the medical record abstraction form is included with this document (Appendix 1).

Off-Label Use Definition

The definition of off-label use of MabThera will be based on the use for a non-oncology disease or medical condition other than RA and GPA/MPA covered by MabThera SPC.

In absence of labelled indications, potential off-label use could include, but is not limited to, the following conditions:

- Ankylosing spondylitis
- Psoriatic arthritis
- Undifferentiated spondyloarthritis
- Juvenile idiopathic arthritis
- SLE
- Systemic vasculitis

- Eosinophilic GPA
- Inflammatory myopathies
- Behçet disease
- Sjögren syndrome
- Nephrotic syndrome
- Glomerulonephritis
- Multiple sclerosis/neuromyelitis optica
- · Pemphigus vulgaris
- Polydermatomyositis
- · Mixed connective tissue disease

Patient Survey data

The patient questionnaire has been developed following standard survey methodological principles and will be cognitively tested with patients in each of the target countries. Modifications will be made to the questionnaire based on the results of testing, and some variations to the questionnaire are anticipated based on country-specific requirements.

The questionnaire will include an introductory section with questions to confirm eligibility. The majority of the questionnaire items will be closed ended, ensuring that the resulting data are easy to analyse and interpret. Closed-ended questions are generally more efficient than open-ended questions (or open-ended text fields) and more conducive to summarisation and statistical analyses.

The questionnaire will collect the following information (please refer to Appendix 1 for the draft questionnaire):

- Demographics (e.g., age, sex, ethnicity)
- Patient previous history of PML or other serious infectious diseases
- Whether the patient has received a previous treatment with MabThera, if so, number of prior infusions during the last 12 months
- Patient understanding or awareness of the following:

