8.6 DATA ANALYSIS

Analysis of MabThera off-label use and evaluation of PAC knowledge and utilisation will be descriptive in nature and will entail the tabular display of summary statistics and the frequency distribution of item responses.

A detailed analysis plan describing methods of analysis and presentation, as well as table shells, will be developed prior to starting analysis of data. In addition to describing the analysis of off-label use, for the questionnaire data, the analysis plan will describe any planned comparisons of participants and non-participants. The analysis plan will also describe the following:

- Analysis of subgroups
- · Methods for handling missing data
- Level of statistical precision

All analyses will be performed using SAS 9.2 (or higher) statistical software (SAS Institute Inc., Cary, North Carolina, USA). Programs, logs, and output will be reviewed for accuracy according to relevant standard operating procedures.

The analysis of off-label use will be descriptive and will present MabThera utilisation by indication (RA, SLE/LN, other). Results will be evaluated by site characteristics, including country and geographic region within country, to ascertain any patterns of prescribing by specific indication. The main analysis will be to estimate (with 95% CIs)

^a With an average cluster size of 8 patients, correlation coefficients of 0.15 and 0.30 correspond with design effects of 2.05 and 3.1, respectively.

^b The percentage in this column does not need to represent only the percentage of correct responses; it can represent any percentage, for example percentage of abstractions that were identified as off-label use or percentage of abstractions that had systemic lupus erythematosus (SLE).

the proportion of off-label use among users of MabThera during the entire study period in the 5 European countries of interest. The proportion of each of the most common off-label use indications will be described among the entire off-label use group. In addition, an estimate of off-label usage will be determined amongst prevalent (i.e., repeat infusions) and incident (i.e., patients attending for their first MabThera infusion) patients to the extent that incident use can be accurately determined. Characteristics of patients meeting the definitions for both strict and broad on-label use will also be evaluated. The dosage of MabThera used by infusion will also be estimated in the on- and off-label groups.

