RA1.	☐ Yes☐ No	•	A1, contin	nue with	RA1	a. If n	o, go to RA2. otrexate use:
		/	/		(dd/n	nm/yy	уу)
RA2.	ever take		ur necrosi	s factor	-alph	a inhi	treatment cycle, did the patient bitors (adalimumab, iximab)?
in time		r to the dat					ts for tests performed closest ion in the patient's current
RA3.	C-reactive	ve protein (CRP) leve	el at first	t Mab	Thera	infusion in the current
	treatmer	nt cycle:		mmol	/L		
	RA3a.	Date of CI	RP test:	/		/	(dd/mm/yyyy)
RA4.	Erythroc	yte sedime	ntation rat	te (ESR) at fi	rst Ma	abThera infusion in the current
	treatmer	nt cycle:	mm/h	r			
	RA4a.	Date of ES	SR:	/	/		(dd/mm/yyyy)

RA5.	Tender j	oint count (0 – 28) at first Mab	Thera infu	ısion in t	he current	treatment
	cycle:	joints				
	RA5a. (dd/mm/	Date of tender joint count:	/	/		
RA6.	Swollen	joint count (0 - 28) at first Mat	Thera inf	usion in	the curren	t treatment
	cycle:	joints				
	RA6a. (dd/mm/	,	/	/		
RA7.		e of extra-articular involvemen reatment cycle:	t at first M	labThera	a infusion i	n the
RA8.		ssessment of patient's genera) at first MabThera infusion in				scale (VAS)
		mm				
	RA8a. (dd/mm/	Date of global health assessr	ment:	/	/	

Medical Record Abstraction Form—Draft

For questions RA9 through RA14a, please provide results for tests performed on or nearest to the date of the patient's most recent MabThera infusion (Q6).

RA9. C-reactive protein (CRP) level at most recent MabThera infusion:

mmol/L Date of CRP test: RA9a. (dd/mm/yyyy) RA10. Erythrocyte sedimentation rate (ESR) at most recent MabThera infusion: mm/hr RA10a. Date of ESR: (dd/mm/yyyy) RA11. Tender joint count (0 - 28) at most recent MabThera infusion: joints RA11a. Date of tender joint count: (dd/mm/yyyy) RA12. Swollen joint count (0 - 28) at most recent MabThera infusion: joints RA12a. Date of swollen joint count: (dd/mm/yyyy) RA13. Presence of extra-articular involvement at most recent MabThera infusion: ☐ Yes □ No

	sessment of patient's general health or at most recent MabThera infusion:	n visu	al ar	nalogu	e scale	(VAS)
	mm					
RA14a. (dd/mm/y	Date of global health assessment:	/		/		

3. Patient Questionnaire - Draft

MabThera Risk Minimisation Programme Evaluation

Patient Questionnaire—Draft

Thank you for agreeing to participate in this study.

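### Section 8.3 defines off-label use by disease alone, against the protocol's own statement of the label and its named classification variables, so the main proportion can only equal or understate label-based off-label use

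*Protocol*

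**What the plan says.** - **Operative definition.** Protocol Section 8.3, under its off-label heading: "The definition of off-label use of MabThera will be based on the use for a non-oncology disease or medical condition other than RA and GPA/MPA". The sentence ends with a reference to the SPC. The list that follows consists only of other diseases.
- **Label for RA.** On the current EU label, Section 6.2 says that it "authorises MabThera in combination with methotrexate for the treatment of adult patients with severe, active RA who have had an inadequate response or intolerance". The earlier treatment meant here is of the disease-modifying kind, with a further condition: "including one or more tumour necrosis factor (TNF) inhibitor therapies".
- **Label for GPA/MPA.** Section 6.2 describes severe, active disease in adults, treated together with glucocorticoids to induce remission.
- **Classification variables.** The list of medical record data in Section 8.3 contains "Methotrexate (key variable for on- or off-label classification of MabThera use") and "TNF-alpha inhibitors (key variable for on- or off-label classification of MabThera use").
- **Main analysis.** Section 8.6 makes the off-label proportion, with its 95% CI, the main estimate. It adds: "Characteristics of patients meeting the definitions for both strict and broad on-label use will also be evaluated". Neither term is defined in the protocol.
- **Supporting places.** Section 8.5 speaks of whether the disease indication represents on- or off-label use. The ENCePP checklist in Appendix 1 (comment to its Section 6) bases the endpoint on clinical indication.

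**The concern.** A variable cannot be key to a classification whose rule leaves it out. Under the rule in Section 8.3, an RA patient with no methotrexate or no earlier TNF inhibitor is on-label, and so is a GPA/MPA patient treated without glucocorticoids or outside induction. By the label as Section 6.2 states it, such use is off-label.

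Specific aim 1 is to quantify and characterise off-label use, and the regulator's request quoted in Section 6.2 rests on the product's off-label potential. If the protocol does not say which definition drives the headline proportion, readers cannot tell what it measures, and the choice could be made after the data are seen.

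**Working it through.** **Inputs**
- n = 1,500 and 75% on-label, hence 25% off-label: the precision example in Section 8.5. It is an example, not an expected value.
- Design effect = 1 + (8 − 1) × ICC, which gives 2.05 at ICC 0.15 and 3.1 at ICC 0.30: Table 1 and its note on an average of 8 patients per cluster.
- f = share of RA and GPA/MPA patients who miss at least one label condition. The documents give no value; 0% to 40% is assumed here.

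**Step 1: reproduce the protocol's interval.** Half-width = 1.96 × √(p(1 − p) × design effect / n).
- No clustering: 1.96 × √(0.75 × 0.25 / 1,500) = 2.19 points, so 72.8% to 77.2%, as in Section 8.5.
- ICC 0.15: 2.19 × √2.05 = 3.14 points, so 71.9% to 78.1%, as in Table 1.
- ICC 0.30: 2.19 × √3.1 = 3.86 points, so 71.1% to 78.9%, as in Table 1.

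The arithmetic of the plan is sound. The issue is the definition.

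**Step 2: direction.** A disease-only rule can move patients who miss a label condition only from off-label to on-label. Disease-based off-label use is therefore never above label-based use, and the two are equal only when f = 0.

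**Step 3: size, as an illustration.** Label-based off-label share = 25% + 75% × f. The labelled-disease group in the example has 0.75 × 1,500 = 1,125 patients.

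| f (assumed) | Label-based off-label use | Gap to 25% (points) |
|---|---|---|
| 0% | 25.0% | 0 |
| 5% | 28.8% | 3.8 |
| 10% | 32.5% | 7.5 |
| 20% | 40.0% | 15 |
| 40% | 55.0% | 30 |

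**Step 4: when the gap exceeds the planned precision.** The gap 75% × f exceeds the half-width once f passes half-width / 0.75.
- No clustering: 2.19 / 0.75 = 2.9%, about 33 of 1,125 patients.
- ICC 0.15: 3.14 / 0.75 = 4.2%, about 47 patients.
- ICC 0.30: 3.86 / 0.75 = 5.1%, about 58 patients.

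These thresholds use Table 1's cluster size of 8. Section 8.5 projects 20-30 records per centre. At 30 and ICC 0.30 the design effect is 1 + 29 × 0.30 = 9.7, the half-width 2.19 × √9.7 = 6.8 points and the threshold 6.8 / 0.75 = 9.1%. That changes the comparison with precision, but not the direction in Step 2.

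**Step 5: can the draft form support a label-based class?** For RA, the supplement in Appendix 1 has a methotrexate item, a prior TNF inhibitor item and the DAS28 components, and the main form has the reason for prescription. For GPA/MPA there is no item on severity or on induction, and glucocorticoids appear only in a 12-month medication checklist that is not tied to the infusion.

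**The case against.** The strongest reply is that a label-based class was probably intended. The reference to the SPC at the end of the definition can be read as limiting RA and GPA/MPA to labelled use, and identifying strict on-label patients under Section 8.6 requires more than the disease. Section 8.6 also defers the detail of the off-label analysis to an analysis plan that is not shown, where an operational algorithm would often sit. A disease-based proportion, labelled as such, is a legitimate quantity, and it answers the one concern that Section 6.2 singles out, prescribing for SLE and lupus nephritis.

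Much of this stands as evidence of intent. It does not settle the conflict. The list under the definition, the wording in Section 8.5 and the checklist all favour the disease-only reading. The strict and broad terms are attached to patient characteristics, not to the main proportion. The protocol itself fixes the definition, so this is not simply a detail left to an analysis plan. Nor can an analysis plan supply GPA/MPA data that were never collected.

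A reader might go further and infer that the study cannot detect RA use outside the label. The documents do not support that, because the RA items are collected and results are shown by indication, so RA use can be reclassified at analysis. A reader might also infer that RA without methotrexate or a TNF inhibitor is the likeliest off-label use. Nothing in the documents says so.

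**Conclusion.** The conflict is real and bears on the main estimate of specific aim 1. The definition in Section 8.3 does not use the variables that the same section calls key, and it is wider than the label set out in Section 6.2. The headline figure would be equal to or below label-based off-label use.

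The direction follows by construction. The size does not: it rests on an assumed f and on a 75%/25% split that the protocol uses only to show precision. Across f from 0% to 40% the gap runs from 0 to 30 points, and a small f, about 3% to 5% on the protocol's own design effects, is enough for it to exceed the planned half-width. It would go too far to call the result falsely reassuring, because the documents do not show that any particular share of RA or GPA/MPA patients falls outside the label.

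**What to change.** Reconcile Sections 6.2, 8.3 and 8.6 and the checklist comment in Appendix 1.

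1. In Section 8.3, define broad on-label use (by disease) and strict on-label use (all label conditions as Section 6.2 states them). For RA, build the strict class from the methotrexate, prior TNF inhibitor, reason-for-prescription and DAS28 data already on the form.
2. State which definition gives the main estimate. Report the other beside it, with a 95% CI.
3. Show patients who are not classifiable as their own category, in line with the data-not-available option in Section 8.3.
4. For GPA/MPA, either add items on severity, induction and glucocorticoid use at the infusion, or state that strict classification is not possible for that group.

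This classifies use against the protocol's own account of the label and sets no clinical rule. The cost is a revised definition, a few form items, one extra table and a reported figure that may be less favourable.

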8.4 PATIENT, STUDY, AND SITE DISCONTINUATION

8.4.1 Withdrawal from Study

Patients may withdraw consent and discontinue participation from the study at any time, with no effect on their medical care or access to treatment. If a patient is withdrawn prior to completing the study, any known reason for withdrawal should be documented in the eCRF. All information already collected as part of the study will be retained for analysis; however, no further efforts will be made to obtain or record additional information regarding the patient.

Every effort should be made to obtain information on patients who withdraw from the study. The primary reason for withdrawal from the study should be documented on the appropriate eCRF page. Patients will not be followed for any reason after consent has been withdrawn. Patients who withdraw from the study will not be replaced.

8.4.2 Study and Site Discontinuation

The Sponsor has the right to terminate this study at any time. Reasons for terminating the study may include, but are not limited to, the following:

- · Patient enrolment is unsatisfactory
- Other reasons

The CRO will notify the physician if the study is placed on hold, or if the Sponsor decides to discontinue the study.

The CRO may replace any site as needed. Reasons for replacing a site may include, but are not limited to, the following:

- Excessively slow recruitment
- Poor protocol adherence
- Inaccurate or incomplete data recording
- Non-compliance with the Guidelines for Good Pharmacoepidemiological Practices (GPP) or any other pertinent local law or guideline

8.5 STUDY SIZE

The results from the feasibility evaluation showed that some large centres recruited more than 100 patients. To avoid large centres being overrepresented in the study population, it is planned to put a cap of 30 patients as the maximum number of patients that a single centre can recruit for either the medical record abstraction component or survey component of the study. To compensate for the 30-patient cap, the recommendation in the feasibility evaluation was to recruit 10-15 infusion centres per country in order to accomplish the recruitment targets for both components of the study.

Medical Record Abstraction Component Study Size

From the estimates obtained in the feasibility evaluation, the Sponsor projects that 20-30 patients per infusion centre will be recruited for the medical record abstraction component of the study, yielding a total of between 1,000 and 1,500 medical records collected during the 10-month period. Because the sample size for the medical record abstraction component of the study will be larger than that for the survey component, there will be greater precision around the estimates of MabThera use by whether the disease indication (RA, SLE/LN, other) represents on-label or off-label use. For example, with a sample of 1,500 patients, if 75% those abstracted are identified as on-label use, then the 2-sided 95% confidence interval (CI) will be 72.8% to 77.2%.

Survey Component Study Size

Considering the estimates of the volume of patients available that were provided by the feasibility evaluation, during a 10-month period, a maximum of 720 patients could be recruited for the survey component in the 5 countries, assuming a mean (median) of 23-24 (13-18) patients per centre and 30 participating centres. However, the mean is based on some large centres recruiting more than 100 patients. To avoid large centres being overrepresented in the study population, it is planned to put a cap of 30 patients as the maximum number of patients that a single centre can recruit. The final study size has been set at 500 completed surveys across all countries, with an estimated 10-14 patients recruited per infusion centre for the survey; this will allow reasonable precision around estimates of patient knowledge and understanding of the PAC at the study level. Since it is planned to recruit up to 10-14 patients per infusion centre for the survey, the responses from patients within the infusion centre may be correlated. Assuming no correlation and the percentage of correct responses to a question (or the percentage with off-label use) is 75%, then for a sample of size 500, the 2-sided 95 CI will be 71.2% to 78.8%; whereas the corresponding CI will be 68.3% to 81.7% if there are on average 8 patients per infusion centre with an intra-class correlation of 0.3. A correct response rate of 50% yields the widest possible CI and thus the least precision; the farther the percentage is from 50%, the greater the precision. Table 1 shows 95% confidence limits assuming various combinations of sample size, percentage with correct response, and intra-class correlation coefficients.

Table 1 Confidence Limits for Various Combinations of Sample Size and Correct

Response Percentage

Patient Sample Size	Intra-class Correlation Coefficient ^a	Correct Response ^b (%)	Lower 95% Confidence Limit (%)	Upper 95% Confidence Limit (%)
100	0	25	16.5	33.5
100	0	50	40.2	59.8
100	0	75	66.5	83.5
100	0	90	84.1	95.9
100	0.15	25	12.8	37.2
100	0.15	50	36.0	64.0
100	0.15	75	62.8	87.2
100	0.15	90	81.6	98.4
100	0.3	25	10.1	39.9
100	0.3	50	32.7	67.3
100	0.3	75	60.1	89.9
100	0.3	90	79.6	100.0
500	0	25	21.2	28.8
500	0	50	45.6	54.4
500	0	75	71.2	78.8
500	0	90	87.4	92.6
500	0.15	25	19.6	30.4
500	0.15	50	43.7	56.3
500	0.15	75	69.6	80.4
500	0.15	90	86.2	93.8
500	0.3	25	18.3	31.7
500	0.3	50	42.3	57.7
500	0.3	75	68.3	81.7
500	0.3	90	85.4	94.6
1500	0	25	22.8	27.2
1500	0	50	47.5	52.5
1500	0	75	72.8	77.2
1500	0	90	88.5	91.5
1500	0.15	25	21.9	28.1

Patient Sample Size	Intra-class Correlation Coefficient ^a	Correct Response ^b (%)	Lower 95% Confidence Limit (%)	Upper 95% Confidence Limit (%)
1500	0.15	50	46.4	53.6
1500	0.15	75	71.9	78.1
1500	0.15	90	87.8	92.2
1500	0.3	25	21.1	28.9
1500	0.3	50	45.5	54.5
1500	0.3	75	71.1	78.9
1500	0.3	90	87.3	92.7

Note: Table calculations assume an average of 8 patients from each practice (cluster).

Calculations performed using SISA software, prevalence module. Uitenbroek DG. Binomial. SISA. 1997. Available at: http://www.quantitativeskills.com/sisa/calculations/preval.htm. Accessed 11 June 2012.

